Appendix 1: Acronyms

AAP, Angiographic Assessment Program; ACE, angiotensin converting enzyme; BARI, Bypass Angioplasty Revascularization Investigation; BMDP, Bio-Medical Data Program; CABG, coronary artery bypass graft surgery; CAD, coronary artery disease; CASS, Coronary Artery Surgery Study; CC, Coordinating Center; CCSC, Canadian Cardiovascular Society classification; CEL, Central Electrocardiographic Laboratory; CRL, Central Radiographic Laboratory; DBMS, Data Base Management System; ECG, electrocardiogram; EF, ejection fraction; ETT, exercise treadmill testing; IMA, internal mammary artery; LAO, left anterior oblique; LV, left ventricle; MC, Minnesota Code; MI, myocardial infarction; MMCC, Morbidity and Mortality Classification Committee; NHLBI, National Heart, Lung, and Blood Institute; NIH, National Institutes of Health; PI, Principal Investigator; PTCA, percutaneous transluminal coronary angioplasty; RAO, right anterior oblique; SAS, Statistical Analysis System; SDMB, Safety and Data Monitoring Board; SEQOL, Study of Economics and Quality of Life; SPSS, Statistical Package for the Social Sciences; TIMI, Thrombolysis in Myocardial Infarction.

Appendix 2: Bypass Angioplasty Revascularization Investigation Glossary of Definitions

Canadian Cardiovascular Society Classification of Angina

Class I: Ordinary physical activity does not cause angina, such as walking and climbing stairs. Angina occurs with strenuous or rapid prolonged exertion at work or recreation.

Class II: Slight limitation of ordinary activity, such as walking or climbing stairs rapidly; walking uphill; walking or stair climbing after meals; the limitation of ordinary activity in cold or windy weather, while under emotional stress, or during the few hours after awakening; walking more than two blocks on a level

surface; or climbing more than one flight of ordinary stairs at a normal pace and under normal conditions.

Class III: Marked limitation of ordinary physical activity, such as walking one to two blocks on a level surface or climbing one flight of stairs under normal conditions and at a normal pace; comfortable at rest.

Class IV: Inability to carry on any physical activity without discomfort. Anginal syndrome may be present at rest.

Clinically Severe Angina or Ischemia

Clinically severe angina or ischemia involves any of the following conditions: 1) non-Q wave myocardial infarction stabilized 4 hours to 6 weeks; 2) unstable angina stabilized 4 hours to 6 weeks; 3) stable CCSC III or IV angina; 4) stable CCSC I or II angina and one or more of the following: a) *severe ischemia on noninvasive testing*, b) Q wave MI (stabilized for 24 hours, revascularization clinically indicated, and ability to randomly assign patients within 30 days after MI), c) resting ejection fraction <50%, d) a history of stable class III or IV angina and current intensive medical therapy (with exercise testing waived); 5) no angina but *severe ischemia on noninvasive testing* and prior Q wave MI; 6) no angina within 6 weeks of study entry but a history of prior angina, with current *severe ischemia on noninvasive testing*.

Definite Q Wave Myocardial Infarction

A definite Q wave MI involves the two-step worsening of Minnesota code Q waves, as determined by the CEL.

Multivessel Coronary Disease

The BARI definition of multivessel coronary disease requires that two or more myocardial territories (anterior, lateral, inferior/posterior) be jeopardized. Therefore, the following definition could also be termed multiterritory disease. To be eligible for BARI a patient must have a 50% or greater diameter reduction by caliper measurement in arteries that supply at least two of the three major myocardial territories (Table 1, Figure 3). These arteries must be >1.5 mm in diameter adjacent to the site of the stenoses. Assignment of coronary segments to a specific myocardial territory (anterior, lateral, inferior/posterior) includes consideration of coronary artery dominance (Table 1).

TABLE 1. Coronary Segments*

Myocardial territory	Right dominant	Left dominant	Balanced
Anterior	12-17, 29	12-17, 29	12-17, 29
Lateral	18-22, 28	18-22, 28	18-22, 28
Inferior/posterior	1-9	23-27	1-5, 23-26

*See Figure 3.

[figure not shown]

FIGURE 3. Coronary artery map. Right coronary artery: 1, proximal; 2, middle; 3, distal; 4, posterior descending; 5, right posteroatrioventricular; 6, first posterolateral; 7, second posterolateral; 8, third posterolateral; 9, inferior septal artery; 10, acute marginal artery. Left coronary artery: 11, left main; 12, proximal left anterior descending; 13, middle left anterior descending; 14, distal left anterior descending; 15, first diagonal; 15a, first diagonal branch; 16, second diagonal; 16a, second diagonal branch; 17, anterior septals; 18, proximal circumflex; 19, middle circumflex; 19a, distal circumflex; 20, 21, 22, first, second, and third obtuse marginal; 20a, 21a, 22a, first, second, and third obtuse marginal branches; 23, left atrioventricular; 24, 25, 26, first, second, and third posterolaterals; 27, left posterior descending; 28, ramus; 28a, ramus branch; 29, third diagonal; 29a, third diagonal branch.

Myocardial Ischemic Response (End Point Definition)

A myocardial ischemic response is indicated by any of the following exercise-induced ECG responses: 1) horizontal or downsloping ST segment depression ≥ 1 mm 80 msec after the J-point; 2) a slow upsloping ST segment depressed ≥ 1.5 mm 80 msec after the J-point; and/or 3) ST segment elevation ≥ 1 mm 80 msec after the J-point in a non-Q wave lead, each as compared with the rest tracing.

New Technology Devices

New technology devices include those currently holding Investigational Device Exemption status and any one deemed "new technology" by the New Technology Committee. Some examples are stents, atherectomy, and laser catheters. (See pp V-3-V-6, Angioplasty Guidelines.)

Severe Ischemia on Noninvasive Testing (Entry Criteria Definition)

Severe ischemia on noninvasive testing is defined as the results of testing as listed herein: 1) Exercise treadmill testing: exercise-limiting definite angina, with final exercise stage less than Bruce stage 3; and exercise-induced **severe ST segment response**, with a final exercise stage less than Bruce stage 3. In addition, patients who do exercise in Bruce stage 3 may also be considered for random assignment if the ischemic changes occur within the first 6 minutes and the patient is judged to be a candidate for revascularization. 2) Exercise ^{201}Tl : multiple reversible defects, increased lung uptake and a single reversible or

fixed defect, and one fixed defect and one reversible defect remote from the fixed defect. 3) Persantine ^{201}Tl : multiple reversible defects and one reversible and one fixed defect. 4) Exercise radionuclide ventriculography: resting ejection fraction ≥ 0.50 and exercise ejection fraction < 0.50 , with a decline in ejection fraction of at least 5% in the absence of left bundle branch block or significant arrhythmia; and resting ejection fraction ≥ 0.50 , with a severe ST segment response and work load < 450 kpm.

Severe ST Segment Response

A severe ST segment response may be indicated by any of the following exercise-induced ECG responses: 1) horizontal or downsloping ST segment depression ≥ 1.5 mm 80 msec after the J-point; 2) slow upsloping ST segment depression ≥ 2.0 mm 80 msec after the J-point; and/or 3) ST segment elevation ≥ 1 mm 80 msec after the J-point in a non-Q wave lead, each as compared with the rest tracing.

Suspected Myocardial Infarction

MI is suspected if any episode of chest pain lasts 20 minutes or longer or if there is the occurrence of new Q waves in the ECG or if there is elevation of cardiac enzymes, as well as any other reason to suspect an MI.

Flow Classification (Thrombolysis in Myocardial Infarction): A Randomized Clinical Trial of Tissue-Type Plasminogen Activator (t-PA) in Patients With Acute Myocardial Infarction

Four specific grades of coronary flow rate, as developed in the TIMI study, are given below.

Grade 3 flow. Antegrade flow into the terminal coronary artery segment distal to a stenosis occurs as promptly as anterograde flow into a terminal coronary artery segment proximal to the stenosis. The clearance of contrast material from the distal coronary artery terminal segment is as rapid as clearance from an uninvolved, more proximally located coronary artery segment.

Grade 2 flow. Contrast material opacifies the terminal coronary artery segment distal to the stenosis. However, the entry of contrast material into the terminal coronary artery segment is perceptibly slower than it is into a more proximally located terminal coronary artery segment. Alternatively, the clearance of contrast material from a terminal coronary artery segment distal to a stenosis is noticeably slower than that from a comparable segment that is not preceded by a significant stenosis.

Grades 1 and 0 flow. There is no obvious flow of contrast material beyond the stenosis in question. A small amount of contrast material may penetrate the occlusion (grade 1); however, the contrast material fails to fully opacify the coronary artery beyond the occlusion.

Flow of contrast material not assessable. In this situation there may be competitive flow to a terminal coronary artery segment. For instance, total occlusion in the proximal right coronary artery may be associated with both anterograde (ipsilateral) and retrograde (contralateral) collateral flow to the distal right coronary artery bed. There may be relatively faint visualization of the distal right coronary bed by the anterograde collateral flow and also by retrograde collateral flow. In this situation it is not possible to accurately assess the flow rates of contrast material in the terminal right coronary artery bed because of the competitive nature of flow. It may also be impossible to judge relative flow in a proximal total occlusion in which collateral flow to the terminal coronary segments is poor. If the terminal coronary segments in this situation are poorly visualized, the correct judgment concerning perfusion may be unclear, and this choice should be indicated.

Appendix 3: Sample Size

Mortality was used as the basis for selecting the sample size for the trial. For PTCA (a procedure less invasive than CABG) to be recommended as an initial revascularization strategy, it is of primary importance to know that the long-term results with PTCA are not appreciably worse than with CABG in terms of mortality. With this in mind, the basis of the BARI sample size calculation was to choose a sample size large enough so that, with a high probability, the upper confidence limit for the absolute difference between PTCA and CABG mortality rates would not exceed a specified value.⁵ This specified value represents the maximum acceptable absolute difference between the CABG and PTCA event rates. In BARI the specified value was taken to be 2.5%, in light of the estimated 5% mortality rate discussed below. In

other words, the sample size was chosen in such a way that if the two strategies were in fact identical in terms of mortality, the study would have a high probability of ruling out excess mortality of 2.5% or more in the PTCA group relative to the CABG group.

Review of the data from the National Heart, Lung, and Blood Institute PTCA Registry and the CASS Trial and Registry indicates that for patients with multivessel CAD, a 5-year mortality rate of 5% after either therapy was a reasonable estimate. For the purpose of calculating sample size, we assume this to be the true common mortality for both PTCA and CABG patients in BARI. Under this assumption, a sample size of 2,400 patients (1,200 assigned to each treatment) yields a probability of 88% that the upper 95% confidence limit for the true difference between the 5-year mortality rates of PTCA and CABG will not exceed 2.5%. Note that if the upper confidence limit of the true difference is 2.5%, then the observed difference must be appreciably less than 2.5%. For example, if the observed 5-year mortality rates were 5.9% for PTCA and 5% for CABG, the observed difference would be 0.9% and the upper 95% confidence limit for the true difference would be 2.4%.

Appendix 4: Random Assignment

Stratification

The sequence of random assignment is stratified by clinical center. This allows for approximately equal allocation of the two treatments within each center as well as preservation of the overall balance between the two treatment groups.

Because of the large number of patients anticipated (1,200 for each treatment), the probability of serious imbalance in the distribution of risk factors is unlikely. In case of such an occurrence, adjustment can be accomplished during the analysis. This can be done without a significant loss of efficiency, and it is preferable to the administratively more complex process of stratifying during random assignment. Therefore, the sequence of random assignment is stratified by clinical center only, and other clinically important factors will be adjusted for (if necessary) in analyses after random assignment.

Design of Random Assignment

The BARI clinical trial requires a scheme of random assignment that will provide a balance in the total number of patients assigned to each treatment group both early and late in the trial. Early balance is necessary to maximize the power to detect differences for safety-monitoring purposes and to adjust for any early learning curve effects in the trial. To achieve this balance, a blocked scheme of random assignment has been implemented, with generation of a separate sequence for each clinical center as described below.

Block lengths were selected at random. After this number was chosen, a permutation of this number of

treatment assignments, with half being PTCA and half CABG, were selected at random from all possible permutations. This permutation then became part of the assignment sequence. The process was repeated until the assignment sequence was of a length of 500 or more. (Each center is expected to recruit an average of 175 patients for a trial size of 2,400 patients, but assignment schemes are longer to allow some clinics to recruit more patients in case other clinics fall behind the projected recruitment rates or have to stop recruitment.)

Treatment Assignments

By using the blocked random assignment scheme indicated above, the CC has generated the treatment assignment schemes for all centers. The file with the random assignment sequence for each center is encoded and stored on the same microcomputer that is used for data entry. Because a high level of security is essential for this file, it is encrypted on each microcomputer to ensure that there is no unauthorized access to these blinded data. Security issues are discussed further on p V-13 (Data Management).

When a patient is to be randomly assigned, the clinic coordinator uses the software developed for random assignment. The coordinator is prompted with a list of questions that reflect BARI trial inclusion and exclusion criteria. Answers to these questions must match the entry criteria (i.e., BARI eligibility must be verified) before the program will indicate that the patient is indeed eligible and provide the patient's treatment assignment. The CC closely monitors the use of the random assignment program.

A contract is maintained at all centers to guarantee service within 4 hours of notification of computer breakdown. The CC is available to assign treatments by telephone in the event that computer repair is delayed. Copies of each random assignment sequence are stored at the CC in secured computer files.

Appendix 5: Complications

Abrupt Closure (Regardless of Previous Dilatation)

There is clinical evidence of one or more coronary arteries abruptly closing.

Arterial Embolus of Extremity or Permanent Loss of Pulse

Acute occlusion of a main or distal arterial trunk supply in a limb assessed by the lack of detectable distal arterial pulsations (by pulsation or Doppler examination) that had previously been observable. The loss of pulse may or may not be associated with ischemia of the affected limb.

Cardiogenic Shock

Hypotension (systolic blood pressure of less than 80 mm Hg) that is associated with reduced urine output, decreased mental acuity, and compensatory vasoconstriction.

Cardiac Tamponade

Hemodynamic compromise, with hypotension and low cardiac output secondary to increased pericardial pressure.

Cerebrovascular Accident (CVA)

A focal neurological deficit that is still at least partially evident more than 24 hours after its onset.

Chest Tubes for More Than 5 Days After Surgery (Self-Explanatory)

Coma

Profound depression in the level of consciousness, reflected by the loss of contact with the environment and loss of spontaneous movement. Brain stem activity (respiration and response to deep pain) may or may not be preserved.

Congestive Heart Failure (CHF)

Manifested by one or more of the following features: dyspnea on exertion, edema, fatigue, orthopnea, and/or paroxysmal nocturnal dyspnea. Other findings that support the clinical diagnosis include the presence of an S3 gallop, elevated jugular venous pressure, and radiographic evidence of pulmonary congestion. Verification by a physician's statement in the medical record is required.

Deep Wound Infection

Positive culture from the mediastinal tissues beneath the sternum.

Dementia

Broad-based loss in higher intellectual function (including cognitive, perceptual, calculational, and/or recall functions) that is evident to family members and close associates or demonstrated on serial functional testing.

Hemorrhage

Severe bleeding sufficient to require transfusion of packed red blood cells.

Hypersensitivity Reaction

An allergic reaction to iodine-containing radiographic contrast media or protamine, which is marked by the development of urticaria, wheezing, prolonged hypotension, or laryngospasm.

Hypotension

Reduction in systolic blood pressure to <90 mm Hg or reduction by ≥ 30 mm Hg compared with the baseline value, which persists for more than 1 minute and requires treatment.

Nonfatal Cardiac Arrest That Requires CPR or Countershock (Self-Explanatory)

Postthoracotomy Syndrome

Clinical syndrome of pleuro/pericarditis manifested by chest pain and fever.

Pulmonary Edema (Cardiac)

Acute congestive heart failure resulting in the accumulation of pulmonary interstitial and alveolar fluid, manifested by profound dyspnea, orthopnea, rales, and evidence of pulmonary congestion on chest X-ray.

Pulmonary Embolus

Acute occlusion of one or more branches of the pulmonary arteries with thrombotic material, usually originating from the iliofemoral or pelvic veins, manifested by the abrupt onset of pleuritic chest pain, worsened gas exchange, increased pulmonary artery pressure, or frank hemodynamic collapse.

Renal Failure

Progressively deteriorating renal function requiring dialysis.

Reoperation for Bleeding

Reoperation performed to remedy excessive bleeding after initial surgery.

Respiratory Failure That Includes Noncardiac Pulmonary Edema and Adult Respiratory Distress Syndrome (ARDS)

Inability of the patient to maintain adequate gas exchange during spontaneous ventilation, even with the assistance of supplemental oxygen. In cases where a patient is receiving mechanical ventilatory assistance after surgery, respiratory failure shall be considered the inability to wean the patient from mechanical ventilation within 48 hours of completion of the surgical procedure.

In noncardiac pulmonary edema the same clinical and radiographic appearances that are in cardiac pulmonary edema are present. However, the pulmonary capillary wedge pressure is ≤ 15 mm Hg.

ARDS is the increased interstitial and alveolar lung water resulting from lung injury from any of a variety of causes in the absence of a cardiac etiology.

Superficial Wound Infection

Positive culture from the surgical or PTCA wound site.

Transient Ischemic Attack (TIA)

A focal neurological defect (usually corresponding to a single vascular territory) that spontaneously resolves so that no residual evidence exists within 24 hours.

Wound Dehiscence

The splitting or bursting open of a procedural wound.

Appendix 6: Angiography and Functions of the Central Radiographic Laboratory

Purpose of the Central Radiographic Laboratory

The CRL is responsible for processing all BARI data that relate to angiograms. Through the development and implementation of the AAP, the CRL ensures that angiographic data regarding coronary anatomy and lesion morphology are collected in a standard format across all sites. Angiographic data for all BARI patients are entered into the AAP at each site. In addition, the CRL performs central angiographic readings for all randomly assigned patients. The central readings performed by the CRL will be used in the primary analysis of BARI.

Angiographic Procedural Requirements

Nitroglycerin is usually administered immediately before coronary arteriography. Notations of catheter size, nitroglycerin administration, and projections used are documented on a Procedure Report Form. Multiple standard views are obtained by using caudal RAO and cranial LAO projections of the left coronary artery and paired LAO/RAO projections of the right coronary artery when possible. Six-inch or 7-in. image-intensifier modes are used for standard views. Before PTCA two views are obtained of each lesion, and these views are replicated after PTCA. A left ventricular angiogram in which a 30° RAO view is used is required, and a cranially angulated steep LAO view is also obtained when possible.

Required Angiograms

All angiograms that are performed on BARI patients must be entered into the AAP at the clinical site. Angiograms are assigned to the following categories.

Baseline. The angiogram that is used to document angiographic eligibility for BARI is considered the baseline angiogram. This angiogram must be entered into the AAP within 5 working days of random assignment.

Before and after initial PTCA. For patients that are randomly assigned to PTCA, data must be entered within 5 working days of completion of the procedure.

Intercurrent angiograms. All angiograms that are performed during follow-up, whether they are part of a subsequent revascularization procedure or not, are considered intercurrent angiograms. These must be entered within 5 working days of the angiogram for randomly assigned patients.

Angiographic Data Entry, Management, and Interpretation

The acquisition of angiographic data is performed by using the AAP, a microcomputer and software system that was developed specifically for use in BARI. The AAP provides a uniform format for the

entry and storage of coronary and left ventricular angiographic data at the clinical sites and provides tools (calipers, tables, reports) for clinicians and angiographers at each institution. Electronic calipers are used to measure catheter diameter (as a calibration), lesion diameter, and the diameter of normal reference segments of the vessel proximal and distal to the lesion. The microcomputer system facilitates the electronic transfer of data from the clinical sites to the CRL. The same AAP system is used at the CRL for angiographic interpretation and data analysis. The microcomputer hardware was provided to the original 14 clinical centers and to the CRL by a gift from Hewlett-Packard Co., Palo Alto, Calif.

All baseline, PTCA, and intercurrent films for randomly assigned patients are sent to the CRL by commercial delivery service as soon as possible after patient discharge. Films are read at the CRL and returned within 20 working days whenever possible. Site angiographic readings that entered into the AAP are transmitted to the CRL by way of telephone connections on a weekly basis.

At the CRL evaluation of baseline and intercurrent angiograms is done by a senior angiographer, who reviews coronary vessel distribution, branching, and myocardial territory supplied. Lesions are assessed for location, severity (calipers), and morphology. LV angiography is evaluated by using quantitative methods for the measurement of ejection fraction and regional wall motion. These evaluations are compared with the initial site reading, and if there are no major differences the CRL reading is final. In the case of major differences, the film is read by a second CRL reader and adjudication is performed. Evaluation of PTCA films is performed by a senior angioplasty operator, who reviews the studies for lesion severity and morphology before and after PTCA. The same adjudication procedures that were outlined above are performed during this evaluation.

Quality Control

Angiograms. The CRL reviews all randomly assigned studies for image quality and protocol compliance. Feedback is provided to the site, the angiographer, and the Operations Committee.

PTCA procedures. Films that document PTCA procedures are reviewed to assess PTCA outcome. Films are graded with respect to protocol compliance as well as angiographic findings.

CRL angiographic readings. The CC randomly designates angiographic studies to be reread at the CRL. This rereading is performed in a blind manner to compare the initial CRL reading with the rereading of the same angiogram to determine the amount of variability in the CRL interpretation of specific angiographic variables.

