In addition, BARI will provide much-needed answers to questions concerning the economic and psychosocial aspects of myocardial revascularization. The economic and quality-of-life consequences of PTCA and CABG strategies over a 5-year follow-up period will be compared. BARI will provide estimates of initial and continuing indirect and direct costs of the two procedures and provide measures on quality of life. These critical data are collected in-depth at seven participating BARI centers in an ancillary study of economics and quality of life (SEQOL). This study is funded by the Robert Wood Johnson Foundation, having had initial funding from Advanced Catheter Systems. In addition to SEQOL, data on the number of significant cardiac hospitalizations, employment status, and limitations of activities are collected for all BARI patients. (Also see resource use and quality of life [p V-8].)

Although BARI is designed for the overall comparison of PTCA versus CABG as the initial strategy, it will also provide comparative data for predetermined subgroups, which are defined by the various clinical and angiographic presentations. Clinical subgroups of special interest are those with unstable angina, stable Canadian Cardiovascular Society Classification functional class III or IV angina, or class I or II angina in the presence of either documented ischemia or recent Q wave MI. Angiographic sub-

groups will be defined by the number of significantly stenosed vessels, the number and proportion of myocardial territories with a jeopardized coronary supply, the complexity of the lesion and vessel anatomy, and the degree of left ventricular function.

Aims of the Bypass Angioplasty Revascularization Investigation Registry

The BARI Registry will include eligible patients who refuse random assignment as well as a 5–10% sample of patients who are excluded from the trial based on angiographic criteria. The group of eligible patients who refused random assignment will lend itself to the investigation of selection factors involved in the choice of PTCA versus CABG. In addition, we will be able to compare the results of treatment selected by choice with that selected by random allocation. The Registry patients who are ineligible for random assignment because of angiographic criteria will be used to assess how angiographic exclusion practices differ across sites, which treatment such patients actually receive, and the long-term outcome with the given treatment.

Patient Selection

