Once a patient has been randomly assigned to PTCA, the procedure must be performed within 2 weeks. Clinical information derived from the medical history, physical examination, ECG, and noninvasive stress testing, coupled with the results of coronary and left ventricular cine angiography, determine the strategy to be used for each patient assigned to PTCA. The aim of the procedure is to maximize the effectiveness of PTCA in relieving ischemia and minimizing the risk of procedure-related untoward events. A lesion may be targeted for PTCA if all of the following conditions are met: a stenosis represents a 50% or greater diameter reduction by caliper measurement, the normal vessel diameter adjacent to the site of stenosis is >1.5 mm, and the vessel supplies a sizable region of viable myocardium. Non-significant lesions, lesions located distally or in small arteries, and lesions in arteries that supply areas of infarction are not routinely dilated. For each patient a hierarchy of lesion priority is set in such a way that PTCA is attempted first in lesions that are most likely to be responsible for the patient's ischemia. Before revascularization of a patient in the study, the clinical importance and suitability of each lesion for PTCA is categorized, and a treatment plan is specified by a BARI-certified operator. These data will be used to define patient subsets for analysis of PTCA outcome and to assess operator performance.

Guidelines for the Percutaneous Transluminal Coronary Angioplasty Procedure

For randomly assigned patients, all PTCAs should be performed by a certified BARI angioplasty operator, and the initial PTCA must be performed by a certified BARI operator. An experienced catheterization laboratory staff should assist, and backup cardiac surgical support must be immediately available. Preprocedure medication should include aspi-

rin (unless contraindicated) and other medication deemed appropriate for the clinical status of the patient. Each patient should be fully heparinized during the procedure.

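### The first baseline angiographic reading is not masked or locked before assignment and procedural result can be known, so the judged items behind the angiographic subgroups are open to arm-dependent reading

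*Protocol*

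**What the plan says.** **Site reading.** Appendix 6, Required Angiograms, defines the baseline film: "The angiogram that is used to document angiographic eligibility for BARI is considered the baseline angiogram". The film thus exists before assignment. On when the site must record its reading, the same section says: "This angiogram must be entered into the AAP within 5 working days of random assignment". Nothing requires the entry to be complete or locked before assignment.

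**Central reading.** Under Angiographic Data Entry, Management, and Interpretation in Appendix 6, baseline, PTCA and intercurrent "films for randomly assigned patients are sent to the CRL by commercial delivery service as soon as possible after patient discharge". The section continues: "At the CRL evaluation of baseline and intercurrent angiograms is done by a senior angiographer". PTCA films go to a different role, a senior angioplasty operator. The CRL reading is compared with the site reading; a major difference leads to a second CRL reader and adjudication.

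**Use of the reading.** Appendix 6 states: "The central readings performed by the CRL will be used in the primary analysis of BARI". Aims of the Randomized Clinical Trial defines the angiographic subgroups by number of stenosed vessels, jeopardized territories, "the complexity of the lesion and vessel anatomy, and the degree of left ventricular function". Data Analysis, Subgroups, plans treatment-by-covariate models that include left ventricular function and angiographic risk. The same section of the protocol lists angiographic factors among the baseline characteristics checked for imbalance and possible adjustment, and it compares angiographic change from baseline between arms.

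**Masking.** Blinded reading of angiograms is stated only for replicate reads of random samples (Quality Control/Reproducibility of Measurements, and Quality Control in Appendix 6).

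**The concern.** A variable that defines a subgroup should be fixed independently of the arm. The film itself is, because it predates assignment. The recorded reading need not be.

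Several items in the BARI lesion classes rest on judgment: moderate against excessive tortuosity or angulation, significant calcification, and whether a side branch can be protected. A reader who knows that a patient was assigned to PTCA, or that a dilatation failed, may grade these items differently. Knowledge of a failed dilatation arises almost only in the PTCA arm. Misclassification that depends on arm can create or hide a treatment-by-anatomy interaction, where misclassification equal in both arms would mainly dilute one. The analyses at stake are those meant to show for which anatomy the two strategies differ, together with any covariate adjustment and change-from-baseline comparison that uses the same readings.

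**Working it through.** No sample size or power figure of the plan is involved. The check sets the timing rules side by side and then asks how large an effect could be.

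**1. Site entry.** Entry is due by working day 5 after assignment. PTCA or CABG is due within 2 weeks of assignment. The assignment can always be known at entry. The procedural result can be known only if the procedure comes before the entry, for example procedure on day 1 and entry on day 5.

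**2. CRL reading.** Films leave the site after discharge. For a patient treated in that admission, the baseline film reaches the CRL after the procedure. Whether PTCA films exist for that patient can itself show the arm.

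**3. Link between the two.** The site reading, possibly made with the arm known, decides through the major-difference rule which CRL readings are reopened.

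**4. Masking.** No statement masks the first site reading or the first CRL reading to assignment, procedure films or result.

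**5. Possible size.** Both illustrations assume no true treatment effect, 1,200 patients per arm (Appendix 3) and 40% with complex or high-risk anatomy (assumed), so 480 and 720 per arm. Overall mortality is 5%, as in Appendix 3.

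*(a) Re-rating driven by procedural failure.* Assume 5% mortality in both strata, 10% failed dilatations, 10% mortality after failure, and 30% of non-complex failures re-rated as complex.
- Patients moved: 720 × 0.10 × 0.30 = 21.6; deaths moved: 2.16.
- Complex PTCA: (24 + 2.16)/(480 + 21.6) = 26.16/501.6 = 5.2%.
- Non-complex PTCA: (36 - 2.16)/(720 - 21.6) = 33.84/698.4 = 4.8%.
- CABG is 5% in both strata, so the spurious interaction is about +0.4 points.

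*(b) Up-reading in the PTCA arm only, unrelated to outcome.* Assume mortality of 8% in high risk and 3% in low risk (0.4 × 8% + 0.6 × 3% = 5%). A share q of low-risk PTCA patients is read as high risk. Mortality in the PTCA high-risk stratum becomes (0.4 × 0.08 + 0.6q × 0.03)/(0.4 + 0.6q).

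| q | PTCA high risk | Difference from CABG (8%) |
|---|---|---|
| 5% | 7.65% | -0.35 points |
| 10% | 7.35% | -0.65 points |
| 20% | 6.85% | -1.15 points |

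The low-risk difference stays 0, so these are also the spurious interactions.

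**6. Scale.** The standard error of the interaction, on the strata as first defined, is:
- (a): sqrt(0.0475 × (2/480 + 2/720)) = 1.8 points.
- (b): sqrt(2 × 0.08 × 0.92/480 + 2 × 0.03 × 0.97/720) = 2.0 points.

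The effects are about 0.2 standard errors in (a) and at most 0.6 in (b), with opposite signs. In both, total PTCA deaths stay at 60/1,200.

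**The case against.** The strongest case against the point is that the protocol already contains most of the protection needed.

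- **Reader roles.** The baseline reader is not the reader of the PTCA films. This stands and weakens the hindsight route. It does not close it: no masking between the readers is stated, and the baseline reader also reads intercurrent films.
- **Measurement.** Stenosis severity is measured with electronic calipers, territories follow a segment table, and ventricular function is read by quantitative methods. This stands. The exposure lies mainly in lesion morphology and class and in the judgment of territory supplied.
- **Earlier judgments.** Entry criteria and suitability are settled before assignment, so eligibility is not exposed. The lesion plan is also protected from procedural hindsight, since "Before revascularization of a patient in the study, the clinical importance and suitability of each lesion for PTCA is categorized", although it is not said to precede assignment.
- **Operations manual.** One exists, is not shown, and may specify masking. If so, a sentence in Appendix 6 would confirm it.

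Some stronger readings are tempting but unsupported:

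- *Baseline and PTCA films arrive and are opened as one package.* The protocol gives them one shipping rule and says no more.
- *The quality-control reread is not blind to the arm.* Appendix 6 says only that it is blind, not to what.
- *A false interaction approaches the 2.5-point margin.* Moving 20% of the 36 non-complex PTCA deaths in setting (a) gives 31.2/487.2 = 6.4% against 28.8/712.8 = 4.0%, a gap of 2.4 points. But this re-rates only patients who die within 5 years, while the CRL aims to return films within 20 working days, before most such deaths can be known. A failed dilatation would also move survivors. The 2.5-point margin concerns overall mortality, which reclassification leaves unchanged.
- *The primary result is biased because central readings enter the primary analysis.* The primary comparison is intention-to-treat mortality at 5 years, and without covariate adjustment it uses no angiographic reading.

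**Conclusion.** The point holds in a limited form. The protocol allows the baseline reading, at the site and at the CRL, to be made with the assignment known and sometimes with the procedural result known, and it states no masking of the first reading. What is exposed is the judged part of the angiographic subgroup variables, any adjustment that uses it, and change from baseline. The unadjusted mortality comparison and eligibility are not exposed.

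Neither size nor direction of bias can be established from the protocol. The two illustrations rest entirely on assumed rates of re-reading, differ in sign and stay below one standard error of the interaction. The case for change is therefore that arm-dependent reading is cheap to prevent and hard to correct afterwards. It does not rest on a demonstrated distortion. The conclusion assumes that no masking rule exists elsewhere in the trial's procedures.

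**What to change.** In Appendix 6, Angiographic Data Entry, Management, and Interpretation, require that:

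1. the CRL reads and locks the baseline film before PTCA films, intercurrent films or the site reading are opened, with the reader masked to these and to the assignment;
2. any second read and adjudication of a baseline film is done under the same masking;
3. all angiographic subgroups are defined from that locked reading.

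Where feasible, the site should also complete its baseline entry in the angiographic system before random assignment, or at the latest before the procedure. This is secondary, because the CRL reading is the one analysed. Making the random assignment software withhold treatment until the angiographic entry is locked is not needed: the two run as separate systems, and the gain would be to the site reading only.

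The cost is a fixed reading order and some film handling at the CRL, with no extra readers, and earlier data entry at the site. Clinical management does not change.
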